The development of any Grade 4 or greater toxicity in any subject at any time will prompt a review of safety data by the Sponsor, PI and the DSMB prior to accrual of any additional subjects. It is recognized that Grade 4 events and death can occur in this population due to disease progression. Therefore, dosing will continue for currently enrolled subjects at the occurrence of a grade 4 event according to protocol unless the PI determines the Grade 4 or greater event is definitely or probably related to the study drug. If attribution is assigned to the study drug dosing will be suspended pending review by the DSMB.

In accordance with the 3+3 design, three subjects will be accrued into the first dosing schedule. If during the priming, vaccination and activation steps no ADLT are observed in any of the three subjects, accrual into the next cohort is allowed. If an ADLT occurs in two of the three subjects, no further dose frequency escalation is allowed. If ADLT occurs in one of

the three subjects, three additional subjects will be accrued into the same cohort. If no ADLT occurs within the additional three subjects, accrual into the next cohort can begin. If an ADLT is observed in any of the additional three subjects, no further dose escalation is permitted.

The development of any DLT toxicity in  $\geq$  33% of the accumulated number of subjects in any and all dosing schedules during the Safety Evaluation Period will result in protocol discontinuation.

At the completion of the Safety Evaluation Period for all cohorts, the safety evaluation of Part 1 will be considered completed and all enrollment will be closed. Efficacy evaluation will continue monthly for each subject until death or loss to follow-up.

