# Dosing Schedule A-2: Intradermal and Intravenous Dosing With AlloStim® alone

The priming step: Subjects will receive an ID injection of AlloStim® (0.5 ml) on Days 0, 3, 7, 10 and 14.

The vaccination step: Subjects will receive IV AlloStim® (3 ml) on Day 21.

The activation step: Subjects will receive an IV infusion of AlloStim® (3ml) on Day 28.

The booster step: Subjects will receive two IV booster infusions of AlloStim® (3ml), one on Day 49 and another on Day 77.

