# **Toxicity Monitoring**

Two types of toxicity are assessed for determination of whether a Dose Limiting Toxicity (DLT) has occurred. An acute dose limiting toxicity (ADLT) is assessed within 48h of a dose administration during the priming, vaccination and activation steps of each protocol. Cumulative dose limiting toxicity (CDLT) is assessed during the complete Safety Evaluation Period including any ADLT that occurs in the booster dosing.

An ADLT is defined as the occurrence of any of the following within 48h of dosing:

- Any  $\geq$  Grade 3 local injection site reaction;
- Any  $\geq$  Grade 3 graft vs host disease;
- Any  $\geq$  Grade 3 infusion related symptoms of duration > 2 days;
- Any  $\geq$  Grade 4 infusion reaction of any duration

For any Grade 1-2 acute toxicity, the study drug administration schedule can continue to the next scheduled dose. If an ADLT is observed, the subject will be followed until the toxicity is resolved or the subject is stable. No further dosing for that subject will occur after an ADLT event

A CDLT event is defined as the occurrence of any of the following within the Safety Evaluation Period

- Any  $\geq$  Grade 3 graft vs. host disease
- Any toxicity  $\geq$  Grade 3 that is probably or definitely related to the study drug;
- Any toxicity not present at baseline that occurs at  $\geq$  Grade 4
- Any autoimmune toxicity  $\geq$  Grade 3 not present at baseline

All adverse events (AEs) and serious adverse events (SAEs), regardless of attribution to the study drug, will be coded, graded and become part of the final safety report for each cohort. The DSMB will review the safety data on each cohort and recommend whether to advance enrollment to the next cohort.

The development of any Grade 4 or greater toxicity in any subject at any time will prompt a review of safety data by the Sponsor, PI and the DSMB prior to accrual of any additional subjects. It is recognized that Grade 4 events and death can occur in this population due to disease progression. Therefore, dosing will continue for currently enrolled subjects at the occurrence of a grade 4 event according to protocol unless the PI determines the event is definitely or probably related to the study drug. If attribution is assigned to the study drug dosing will be suspended pending review by DSMB.

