# **12.1.** SCHEDULE DEVIATIONS

Scheduled protocol activities should be conducted on the specified protocol days. In some cases the scheduling may not be able to be followed precisely. For example, subjects may miss appointments causing deviations due to illness, weather, transportation problems or miscommunication. The clinic may experience deviations in scheduling due to lack of available site personnel, lack of available supplies, mechanical or equipment failures. Deviations may also occur due to unavailability of the study drug, due to QC failures or study drug transport problems. In addition, holidays and weekend scheduling may cause conflicts.

If a scheduled protocol appointment is missed for any reason and the study drug has already been shipped, the protocol procedure can be delayed by one or two days, as long as the study drug is delivered within its 72 hours shelf life time. If the study drug cannot be delivered within the 72 hours shelf-life window, then the protocol procedure should be rescheduled for the next available protocol activity day. When rescheduling protocol treatments, the study drug should not be administered within 3 days of a previous study drug administration. Thus, up to a 7 day delay in protocol procedures is allowed for a missed appoint.

For schedule C, the second intratumoral injection after cryoablation (day 17) must occur 3 days +/- 1 day after the ablation procedure.

Schedules for laboratory and research blood tests and follow-up assessments can deviate +/- 3 days from the scheduled protocol days. Schedules for CT scans can deviate +/- 1 week from the protocol days. All protocol deviations should be documented with the reason and the rescheduling clearly stated on a form provided by the Sponsor for this purpose.

If protocol deviations in treatment days occur more than once or occur outside of the allowed deviation windows, the subject will be censored as of the date of the violating deviation for survival analysis.

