#### **13.2.** EARLY DISCONTINUATION OF INDIVIDUAL SUBJECTS

Subjects may discontinue participation in the study for the following reasons:

- Protocol violation
- Withdrawal of consent
- DLT event
- Non-compliance
- Changes in the subject's condition render the subject unacceptable for further treatment in the judgment of the Principal Investigator (the reason(s) must be documented)
- Subject becomes pregnant (withdrawal is required)
- Subject is lost to follow-up

After termination of study therapy, the subject will be treated as clinically indicated by the investigator. All subjects will be followed until resolution or stabilization of any study-related toxicity. If a subject is discontinued from all study therapy, the reason(s) for discontinuation should be documented in the subject's medical record and CRF/eCRF. A follow-up evaluation should be performed approximately 28 days after the last dose of study drug.

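### For a subject with a drug-related Grade 3 CDLT, the next dose is not required to wait, and Section 12.1 censors survival with no exception for a toxicity hold

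*Combined protocol and SAP*

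**What the plan says.** Section 8 (Toxicity Monitoring), like the abstract, includes among CDLTs any toxicity of at least "Grade 3 that is probably or definitely related to the study drug" during the Safety Evaluation Period. No dosing instruction for the affected subject follows from that definition. The neighbouring events do have one. After an ADLT, "No further dosing for that subject will occur after an ADLT event". For a Grade 4 event that the investigator judges probably or definitely related, "If attribution is assigned to the study drug dosing will be suspended pending review by DSMB"; in the abstract, the sentence just before this one names Grade 4 or greater. Section 15.4 ends AlloStim after a Grade 3 or Grade 4 infusion reaction. Section 14.6 removes a subject who receives systemic steroids in the Study Period.

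For the remaining related Grade 3 events the text is permissive. Section 13.2 lists a DLT event, and a change in condition as judged by the investigator, under the opening "Subjects may discontinue participation in the study for the following reasons". Section 14.4.2 lets the duty physician halt, postpone or call off an infusion. Section 15.7 has any DLT prompt a DSMB safety review.

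Section 12.1 governs late doses. It says "Thus, up to a 7 day delay in protocol procedures is allowed for a missed appoint". It then adds "If protocol deviations in treatment days occur more than once or occur outside of the allowed deviation windows, the subject will be censored", for the survival analysis and from the date of the deviation. Illness is among its examples of why a schedule slips; a toxicity hold has no exception. Section 16.1.6 gives a different OS rule (censor at the last date known alive) and does not mention 12.1.

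**The concern.** Safety is the primary endpoint. A related Grade 3 CDLT is grave enough to count toward the rule that discontinues the protocol when 33% of accumulated subjects have a DLT. Yet whether the affected subject gets the next dose is left to case-by-case judgement, while the same attribution one grade higher suspends dosing automatically. Toxicity after a CDLT would then partly reflect individual redosing decisions that the plan does not describe.

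The second matter is statistical. If a dose is held for toxicity, 12.1 as worded can end that subject's contribution to the survival analysis on the date of the hold. Toxicity may well be related to prognosis, so the usual assumption that censoring is unrelated to the risk of death would be doubtful, and later deaths in those subjects would not be counted. This reaches the Grade 4 suspension that Section 8 itself requires: following one section could trigger censoring under another.

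**Working it through.** The plan gives no figure to reproduce; this is a comparison of rules with some simple arithmetic.

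**1. Dosing instruction for the affected subject**

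| Event | Instruction | Where |
|---|---|---|
| Grade 1-2 acute toxicity | may go on to next dose | Section 8 |
| ADLT | no further dosing | Section 8 |
| Grade 3-4 infusion reaction | no further AlloStim | 15.4 |
| Systemic steroids given | removed, data censored | 14.6 |
| Grade 4, probably/definitely related | suspended pending DSMB review | Section 8, abstract |
| Grade 4, not so related | dosing continues | Section 8 |
| Grade 3, probably/definitely related, none of the above | none required; stopping permitted, review prompted | 13.2, 14.4.2, 15.7 |

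An example of the last row is a related Grade 3 liver or blood-count abnormality. The other texts do not fill the gap:
- The list in 13.2 marks withdrawal as required for pregnancy but not for a DLT event.
- The Grade 3 definition in 15.1.3 covers only events not specified in CTCAE, and it accepts additional therapy as an alternative to stopping or reducing the dose.
- The DSMB outcomes in 15.6 concern the study, not one subject.

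**2. Time to the next dose**

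Boosters are left out because their number and optional status differ between sections.
- A-1 mandatory days 0, 7, 14, 21, 28: gaps 7, 7, 7, 7.
- A-2 mandatory days 0, 3, 7, 10, 14, 21, 28 ("on Days 0, 3, 7, 10 and 14", then 21 and 28): gaps 3, 4, 3, 4, 7, 7. If the intradermal days 0, 7, 14 given for A-2 in 14.4.1 were followed, every gap would be 7.

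Section 15.3.1 allows 10 calendar days for a non-serious event to reach the sponsor. Since 10 > 7, the next mandatory dose can come first in either schedule. After Day 28 this no longer applies: the first booster is 56 - 28 = 28 days later in A-1 and 49 - 28 = 21 days later in A-2.

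**3. What the 33% rule adds**

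The smallest k with k/n at or above 0.33 is:
- n = 1-3: k = 1 (1/3 = 33.3%)
- n = 4-6: k = 2 (1/4 = 25% is not enough; 2/6 = 33.3%)
- n = 7-9: k = 3
- n = 10-12: k = 4
- n = 31 (6 + 25): k = 11 (10/31 = 32.3%; 11/31 = 35.5%)

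Read literally, one DLT in the first three subjects stops the whole protocol, although that sits badly with the 3+3 rule that expands a cohort after one ADLT in three. From the fourth subject on, one DLT alone does not.

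**4. When a hold meets the 12.1 censoring rule**

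- Any dose held more than 7 days is outside the window, in either schedule.
- Days from the first missed dose to the next scheduled mandatory dose: A-1, 7 in each case (7→14, 14→21, 21→28). A-2, 4 (3→7), 3 (7→10), 4 (10→14), 7 (14→21), 7 (21→28). Whether one hold that moves two doses is one deviation or two is not stated.
- A single hold of 7 days or less that moves one dose is not censored.

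Part 1 has 3 subjects per schedule, so one censored subject is 1/3 of a schedule.

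**5. Frequency**

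The plan gives no expected rate. The first adverse event table in 6.6.1 shows one Grade 3 event in 42 subjects (1/42 = 2.4%). It appears to be the drug-related table but is not labelled so. If that rate applied here, 31 × 1/42 = 0.74 events would be expected. This is an illustration only.

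**The case against.** The best reply is that the gap is narrow and already covered by judgement and oversight. Infusion reactions, ADLTs and steroid-treated immune events all have mandatory stops. Serious Grade 3 events reach the sponsor within 24 hours and the DSMB at once. Any DLT prompts a DSMB review, and Section 8 expressly grants continuation only after Grade 1-2 acute toxicity. All of this stands. A reader might infer that the protocol directs redosing after a dose-limiting toxicity, or that nothing could stop it. The documents do not support that: stopping is permitted, review is prompted, and the 33% rule can end the protocol. What is missing is only a requirement that the dose wait.

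One might also read the suspension sentence as reaching Grade 3. It closes a paragraph about Grade 4 events, and the abstract makes that limit explicit ("If attribution is assigned to the study drug dosing will be suspended pending review by the DSMB" follows directly on Grade 4 or greater).

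The causality table in 15.1.3 is a fair point. Probable and definite relationship both rely partly on the event easing off drug or between doses, so the attribution may come late. That affects when a hold should start. It does not supply a rule, since easing is not recovery.

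On 12.1, the section mainly concerns missed appointments and logistics, and it allows rescheduling to the next activity day when product cannot arrive within its shelf life. Treating a physician-ordered hold as a deviation is therefore an inference from the wording, though the section does name illness. A reader might infer that any hold, or any 3-4 day hold in A-2 priming, censors the subject. The text does not settle that.

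Finally, a written subject-level DSMB recommendation for every non-serious Grade 3 event would be heavy for a board supplied with data quarterly. That objection is accepted.

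**Conclusion.** The point holds for the affected subject's own dosing. A related Grade 3 CDLT outside the listed categories carries no required hold, and from priming to activation the next dose can fall 3 to 7 days later, before a non-serious event need be reported. The DSMB charter is not among the documents, so the finding is that the protocol is silent, not that no rule exists anywhere.

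The firmer part is 12.1. As worded it can censor survival because of drug toxicity, including after a suspension that Section 8 requires, and it does not agree with 16.1.6. The effect is confined to OS, which Section 9.2 makes exploratory and 16.1.6 summarises descriptively; the primary safety summaries are not censored by it. This rests on reading a toxicity hold as a treatment-day deviation and on the hold exceeding 7 days or being counted more than once. How many subjects would be affected is unknown. Both parts should be corrected; neither undermines the design.

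**What to change.** 1. In 12.1, state that a dose held, delayed or stopped for toxicity, or under a DSMB suspension, is not a treatment-day deviation and does not censor survival, and that OS for such a subject is censored only as in 16.1.6. This costs nothing.

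2. In Section 8 and the abstract, extend the existing suspension sentence to any Grade 3 CDLT:
   - Hold that subject's next dose from the time the investigator suspects a probable or definite relationship, without waiting for dechallenge to confirm it.
   - Report the event to the sponsor within 24 hours, even if non-serious.
   - Resume only after recovery to Grade 1 or baseline and completion of the review that 15.7 already prompts.

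   Refer to this rule in 13.2 and 15.7. A written DSMB recommendation for the individual subject is optional.

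Keep every stricter stop as it is: ADLT, Grade 3-4 infusion reaction and the steroid rule in 14.6.

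The cost is wording in five places, a few delayed doses (some needing a fresh shipment, given the 72-hour shelf life) and faster reporting of a few non-serious events. The sample size does not change.

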#### **Study Duration:**

Part 1 is projected to last 30 to 72 weeks. It is projected that approximately one subject will be accrued every two weeks. Part 2 is projected to last an additional 72-104 weeks Subjects, as long as they are available for follow-up, will be followed monthly for 12 months following last dose administration for survival and quarterly thereafter.

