# Summary of Treatment-Emergent Adverse Events in Subjects Treated with AlloStim $^{\rm TM}$ ITL-002-CRYO

The following table summarizes all AE regardless the causality:

| Adverse Event (CTCAEv3)         | Total # of
Subjects |       | % of Total |       | Grade 1 | Grade 2 |   | Grade 3 |   | Grade 4 | Grade 5 |   |
|---------------------------------|------------------------|-------|------------|-------|---------|---------|---|---------|---|---------|---------|---|
|                                 | n                      | %     | n          | %     | n       | %       | n | %       | n | %       | n       | % |
| Alkaline phosphatase (High)     | 25                     | 59.52 | 15         | 35.71 | 9       | 21.43   | 1 | 2.38    |   | 0       |         | 0 |
| ALT (High)                      | 16                     | 38.10 | 11         | 26.19 | 3       | 7.14    | 2 | 4.76    |   | 0       |         | 0 |
| AST (High)                      | 25                     | 59.52 | 15         | 35.71 | 7       | 16.67   | 3 | 7.14    |   | 0       |         | 0 |
| Allergy, Immunology Reaction    | 41                     | 97.62 | 40         | 95.24 | 1       | 2.38    |   | 0       |   | 0       |         | 0 |
| Anorexia/Decreased Appetite     | 7                      | 16.67 | 4          | 9.52  | 2       | 4.76    |   | 0       | 1 | 2.38    |         | 0 |
| Bilirubin (Hyperbilrubinemia)   | 8                      | 19.05 |            |       | 1       | 2.38    | 5 | 11.90   | 2 | 4.76    |         | 0 |
| Calcium (Hypocalcemia)          | 31                     | 73.81 | 21         | 50.00 | 10      | 23.81   |   | 0       |   | 0       |         | 0 |
| Calcium (Hypercalcemia)         | 2                      | 4.76  | 2          | 4.76  |         | 0       |   | 0       |   | 0       |         | 0 |
| Constipation                    | 7                      | 16.67 | 7          | 16.67 |         | 0       |   | 0       |   | 0       |         | 0 |
| Creatinine (High)               | 5                      | 11.90 | 3          | 7.14  | 2       | 4.76    |   | 0       |   | 0       |         | 0 |
| Distention/Bloating (Abdominal) | 4                      | 9.52  |            |       | 4       | 9.52    |   | 0       |   | 0       |         | 0 |
| Diarrhea                        | 8                      | 19.05 | 7          | 16.67 | 1       | 2.38    |   | 0       |   | 0       |         | 0 |

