In accordance with the 3+3 design, three subjects will be accrued into the first dosing schedule. If during the priming, vaccination and activation steps no ADLT are observed in any of the three subjects, accrual into the next cohort is allowed. If an ADLT occurs in two of the three subjects, no further dosing is allowed. If ADLT occurs in one of the three subjects, three additional subjects will be accrued into the same cohort. If no ADLT occurs within the additional three subjects, accrual into the next cohort can begin. If an ADLT is observed in any of the additional three subjects, no further dose escalation is permitted.

The development of any DLT toxicity in  $\geq$  33% of the accumulated number of subjects in any and all dosing schedules during the Safety Evaluation Period will result in protocol discontinuation.

At the completion of the Safety Evaluation Period for all cohorts, the safety evaluation of Part 1 will be considered completed and all enrollment will be closed. Efficacy evaluation will continue monthly for each subject until death or loss to follow-up.

# Part 2

The safety and efficacy data from Part 1 will be evaluated and the favored schedule advanced to Part 2. In Part 2 of the trial, up to 25 additional subjects may be accrued.

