#### **15.7.** STOPPING RULES

An external DSMB will oversee this study. The investigators and representatives of the Sponsor and DSMB will review and discuss subject data for all subjects enrolled by teleconference. The DSMB could recommend stopping the clinical trial for safety purposes.

The development of dose limiting toxicity (DLT) in any subject will prompt a review of safety data by DSMB. The development of any DLT toxicity in  $\geq 33\%$  of the accumulated number of subjects at any dosing during the assessment period (28 days after last booster infusion) will result in protocol discontinuation. However, if DTLs only occur in the Activation or Booster phase, then a decision by DSMB may be made to continue enrolling subjects to receive only priming and in-situ vaccination phases.

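### In schedule A-1, one acute DLT among the first three subjects triggers both cohort expansion and protocol discontinuation, and the plan does not say which prevails

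*Combined protocol and SAP*

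**What the plan says.** Section 8 (Toxicity Monitoring) and Section 3 define two kinds of DLT. ADLTs are assessed within 48 hours of a dose in the priming, vaccination and activation steps. CDLTs are assessed over the whole Safety Evaluation Period, which runs to 28 days after the last dose. One CDLT criterion carries no attribution condition: "Any toxicity not present at baseline that occurs at" Grade 4 or above.

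Two rules then act on these events.

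- **Cohort rule (3+3, ADLTs only).** No ADLT in three opens the next cohort. For a single event, "If ADLT occurs in one of the three subjects, three additional subjects will be accrued into the same cohort".
- **Protocol rule (any DLT).** A DLT in at least 33% "of the accumulated number of subjects in any and all dosing schedules during the Safety Evaluation Period will result in protocol discontinuation". Section 15.7 repeats the threshold with a different denominator: "of the accumulated number of subjects at any dosing during the assessment period (28 days after last booster infusion) will result in protocol discontinuation".

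Section 15.7 adds one exception: "if DTLs only occur in the Activation or Booster phase, then a decision by DSMB may be made to continue enrolling subjects", and those subjects would receive priming and in-situ vaccination only. Part 1 accrues three subjects to A-1 and then three to A-2, and the planned pace is that "approximately one subject will be accrued every two weeks".

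**The concern.** Both rules are written as mandatory, and the same single event meets both. After one ADLT in the priming or vaccination steps of A-1, the site, the sponsor and the DSMB are told to enrol three more subjects and also to end the protocol. Nothing says which instruction governs, so the choice would be made after the event is known. Safety is the primary endpoint, and these are the main decision rules of Part 1.

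The missing minimum number also affects CDLTs. Section 8 expects Grade 4 events from progression and says that "dosing will continue for currently enrolled subjects at the occurrence of a grade 4 event" unless the event is attributed to the drug. Yet one new Grade 4 event of any cause counts as a CDLT, and while three or fewer subjects have been accumulated it is enough to discontinue the protocol.

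**Working it through.** The plan gives no DLT rate, power or sample-size calculation. Section 16.1.8 rests three per schedule on judgment, so there is no figure to reproduce. The check is a count against the threshold, followed by binomial probabilities at assumed rates.

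**Inputs.** Three subjects in A-1, sequential accrual, and A-2 only after A-1 clears (Section 8). Threshold ≥33% (Sections 3, 8 and 15.7). Pace of one subject per two weeks (Section 3, Study Duration).

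**Step 1: the fraction at each point (subjects with a DLT / accumulated subjects).**

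| Count | Share | 33% rule | 3+3 rule, if all are ADLTs in one cohort |
|---|---|---|---|
| 1/1, 1/2 | 100%, 50% | stop | cohort of three not yet complete |
| 1/3 | 33.3% | stop | add three subjects |
| 2/3 | 66.7% | stop | no further dosing (Section 8) |
| 1/6 | 16.7% | continue | next cohort may open |
| 2/6 | 33.3% | stop | no further escalation |

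The conflict is at 1/3. The expansion that would bring the share down to 1/6 cannot be reached without first passing a point at which the protocol must stop.

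**Step 2: does the Section 15.7 exception remove it?** It applies only if DLTs are confined to activation or booster, which in A-1 means the Day 28 infusion or later. It does not cover an ADLT on Days 0 to 21. Where it does apply it is discretionary and drops the activation step, so it is not the same-cohort expansion.

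**Step 3: CDLTs and timing.** At the planned pace, A-1 subjects start at about calendar days 0, 14 and 28. Subject 3 clears activation at about 28 + 28 + 2 = day 58, and A-2 subjects can then enter at about days 58, 72 and 86. With both boosters, an A-1 subject's Safety Evaluation Period ends on Day 84 + 28 = 112, so subject 3's ends at about calendar day 140. A first CDLT before day 58 is 1/1 to 1/3 and stops the protocol. One after A-2 has opened can be 1/4, 1/5 or 1/6 (25%, 20%, 16.7%) and does not.

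**Step 4: how often, on ADLTs alone.** Let p be the true ADLT rate (assumed).

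- Exactly one in three: 3p(1−p)². At p = 0.05, 3 × 0.05 × 0.9025 = 0.135. At p = 0.10, 3 × 0.10 × 0.81 = 0.243.
- A-1 passes if the 33% rule prevails: (1−p)³ = 0.857 and 0.729.
- A-1 passes if the expansion prevails: (1−p)³ + 3p(1−p)² × (1−p)³. At 0.05, 0.857 + 0.135 × 0.857 = 0.973. At 0.10, 0.729 + 0.243 × 0.729 = 0.906.

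**Step 5: which rates are plausible?** In the all-cause tables of Section 6.6.1 (42 subjects), allergy or immunology reactions (41 subjects) and flu-like symptoms (38) reached no Grade 3, and pain reached Grade 3 once. As a rough proxy, 1/42 = 2.4% gives 3 × 0.024 × 0.976² = 6.8% for exactly one in three. Zero in 42 has a one-sided 95% upper bound of 1 − 0.05^(1/42) = 6.9%.

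**The case against.** The strongest reply is that a protocol-level discontinuation rule naturally outranks a cohort accrual instruction, so there is no real choice. That is a sensible reading, but the text does not state it. If it is right, the expansion branch is dead text in A-1 and the declared 3+3 becomes a zero-of-three rule. A second reply is that the 33% might be computed only when all cohorts have finished. No calculation time is given, so this is possible; but the wording refers to accumulated subjects and does not defer the count.

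The safeguards are real. Any DLT prompts DSMB review, any Grade 4 or worse event prompts review before further accrual, and the DSMB recommends whether each cohort advances. None of these says which rule governs.

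Three stronger readings are tempting and not supported.

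- A reader might infer that every first DLT in A-1 ends the trial. Step 3 shows that this holds for ADLTs and early CDLTs only.
- A reader might apply ADLT rates of 20% or 30%, where exactly one in three has a chance of 38.4% or 44.1%. The documents give no ADLT rate, and Step 5 points to a much lower one.
- A reader might turn the earlier study's five Grade 4 entries ("Bilirubin (Hyperbilrubinemia") 2, anorexia 1, dyspnea 1, lymphopenia 1) into a trigger frequency. They represent 2 to 5 of 42 subjects, which gives 1 − (40/42)³ = 13.6% to 1 − (37/42)³ = 31.6% for at least one in three. That counts events whenever they occur, including after A-2 has opened, so it overstates how often the rule fires. That study also mixed tumour types and graded by CTCAE v3, and its tables do not show what was present at baseline.

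Continued dosing of individual subjects after an unattributed Grade 4 event is also not, by itself, a contradiction of a protocol-level count. The difficulty is that the count has no floor.

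**Conclusion.** The conflict is real and follows from the text: at one ADLT in the first three A-1 subjects, Sections 3 and 8 require both expansion and discontinuation. After an ADLT in priming or vaccination no exception applies. An early CDLT, including a disease-related new Grade 4 event, meets the same threshold while three or fewer subjects are accumulated; a late one may not.

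The chance of meeting the conflict is 13.5% at an assumed ADLT rate of 5% and 24.3% at 10%, and lower still if the earlier study is a fair guide. Which rule prevails then moves the chance that A-1 passes between 0.857 and 0.973, or between 0.729 and 0.906. This rests on the 33% being a running count and on independent events at a constant rate. It merits an amendment because these are mandatory safety rules and the repair is cheap, not because the conflict is likely.

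**What to change.** In Sections 3, 8 and 15.7:

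- Discontinue the protocol when at least two subjects have had a DLT (ADLT or CDLT) and they make up at least 33% of accumulated subjects, pooled across schedules as Sections 3 and 8 already say. The pooling must be stated in 15.7: after a clean A-1, one A-2 event is 1/6 = 16.7% pooled but 1/3 = 33.3% if its wording is read per schedule.
- A single DLT pauses accrual until the DSMB has reviewed it. If it is an ADLT in one of three, the cohort then expands by three.
- State that discontinuation prevails if both rules are met, for example when an ADLT in one subject and a CDLT in another make 2/3.
- Keep the Section 15.7 DSMB option. Use the Section 8 ADLT list in both sections, since Section 3 omits Grade 3 or worse graft-versus-host disease. For two ADLTs in three, use Section 8's bar on further dosing; Section 3 bars only escalation of dose frequency.

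This keeps every present stop that involves two or more subjects (2/3, 2/4, 2/5, 2/6, 3/9), for CDLTs as well, and agrees with 3+3 at 1/6. Two simpler repairs do not work. Changing the threshold to strictly above 33% leaves 33.3% above it. Starting the rule at six subjects would let two or three CDLTs among the first three, such as graft-versus-host disease arising after 48 hours, escape the automatic stop.

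The cost is amendment wording, no added data collection, and up to three more A-1 subjects, whom the 3+3 rule already foresees. The real loss is the automatic stop after a single DLT. On ADLTs alone, the chance that A-1 passes rises from 0.857 to 0.973 at a 5% rate and from 0.729 to 0.906 at 10%. The pause and DSMB review offset that only in part.
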